#### **9.4.9 Immunogenicity Analyses**

The IAS will be used for the immunogenicity analysis.

Immunogenicity analysis samples will be scored ADA positive or ADA negative and subsequently reported. From positive ADA samples, titer values and scores (positive or negative) will be determined and reported. ADA negative samples with drug on board above the drug tolerance limits of the ADA method will be scored inconclusive due to possible drug interference. The association between positive/non-positive ADA and PK ( $C_{max}$ , AUC,  $C_{trough}$ ) and the association between positive/non-positive ADA and major safety signals (CTCAE  $\geq$

grade 3) may be explored. The association with clinical response will be explored in Expansion cohorts only.

#### **9.4.10 Multiplicity**

As the trial does not address a hypothesis per se, there is no multiplicity to correct for.

### **9.5 Interim Analyses**

#### **9.5.1 Expansion Part A – Anti-CD38 mAb-Naive RRMM Cohort**

As outlined in Section 4.1.3, data from the initial 10 anti-CD38 mAb-naive RRMM subjects belonging to the RES who received GEN3014 (at 16 mg/kg or 24 mg/kg) from the Dose Escalation and/or from the Expansion Part A, will be reviewed by the Safety Committee and DMC when they have completed  $\geq 2$  cycles of treatment. If 2 or more out of the initial 10 subjects respond to GEN3014, the comparison vs daratumumab SC will be initiated.

Should the true underlying response rate be 40%, the probability to have 2 or more responders in 10 subjects is 95%. That is, it would be very unlikely to have 0 or 1 responders (in 10 evaluated) under the assumption of a response rate of 40%.

#### **9.5.2 Expansion Part A – R/R DLBCL Cohort**

The maximum sample size in the R/R DLBCL expansion cohort is set to 40 subjects. A non-binding interim futility analysis will be conducted based on the response data from the initial 20 subjects belonging to the RES ([FDA Guidance, 2022](#)). The timing of the interim analysis is when the initial 20 subjects have completed  $\geq 2$  cycles of GEN3014 treatment. The totality of the data (including efficacy, safety, and PK) will be evaluated by the sponsor Safety Committee, which decides if enrollment should be stopped or continued.

The SADAL trial reported an ORR of 28% (36/127; 95% CI 20.7-37.0) ([Kalakonda et al., 2020](#)) which led to approval of XPOVIO in R/R DLBCL subjects. For the purpose of signal finding in heavily pre-treated DLBCL patients the undesirable response rate for GEN3014 is set to 20% and the desirable response rate is set to 40%. With a Simon's 2-stage design (with type I error rate of 4.04% and power of 85.39%) at least 5/20 responders are needed to pass the futility bar. At least 13/40 responders are needed to consider GEN3014 having a potential in DLBCL who have exhausted SOC.

### **9.6 Safety Stopping Guidance for Expansion Cohorts**

Pocock's flexible alpha-spending method will be used as a stopping guidance for each expansion cohort similar to the method described by ([Ivanova et al., 2005](#)), but in a more stage-wise manner. For each individual cohort, the overall significance level to stop further treatment due to safety concern is set to 5%. [Table 9-2](#) through [Table 9-5](#) provide stopping guidance for the different disease cohorts treated with GEN3014 in expansion (does not include subjects treated with daratumumab SC). (The alpha spent will be adjusted if the information rates deviate from the planned.)

For the grade 4 treatment-related AEs, the same acceptable rate of 10% is adopted for all expansion cohorts. For AML, if data indicate a treatment-related death rate exceeding 5%, stopping the expansion cohort will be considered. For MM and DLBCL, if data indicate a treatment-related death rate exceeding 1%, stopping the expansion cohort will be considered.

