**Table 9-2 Stopping Guidance for RRMM anti-CD38 mAb-naïve**

	n=5	n=10	n=20	n=35	n=50
Grade $\geq 4$ Treatment-Related AE (stop if $\geq$ )	4	4	6	8	10
Treatment-Related Death (stop if $\geq$ )	2	2	2	3	3

AE=adverse event; CD=cluster of differentiation; mAb=monoclonal antibody; RRMM=relapsed or refractory multiple myeloma.

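### The 5% safety-stop level is stated per expansion cohort, but each of the two stopping rows has its own 5% budget; the chance of crossing either is 6.6% in naive RRMM, marginally above 5% in DLBCL and AML, and below it in refractory RRMM

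*Protocol*

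**What the plan says.** Protocol 9.6 names the method: "Pocock's flexible alpha-spending method will be used as a stopping guidance for each expansion cohort". It fixes the level per cohort: "For each individual cohort, the overall significance level to stop further treatment due to safety concern is set to 5"%. It gives the acceptable rates as follows.

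- AEs: "For the grade 4 treatment-related AEs, the same acceptable rate of 10% is adopted for all expansion cohorts".
- Deaths in AML: "For AML, if data indicate a treatment-related death rate exceeding 5%, stopping the expansion cohort will be considered".
- Deaths elsewhere: "For MM and DLBCL, if data indicate a treatment-related death rate exceeding 1%, stopping the expansion cohort will be considered".

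Tables 9-2 to 9-5 each print two rows. For naive RRMM, at looks of n = 5, 10, 20, 35 and 50, they are "Treatment-Related AE (stop if $\geq$ ) 4 4 6 8 10" and "Treatment-Related Death (stop if $\geq$ ) 2 2 2 3 3". Nothing in 9.6 divides the 5% between the rows or says that it applies to each. Protocol 9.4.10 states that there is no multiplicity to correct for.

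SAP 5.7.3 repeats the 5% level and the 10%, 5% and 1% rates. Its AE rows all match the Protocol, and so do its death rows for DLBCL and AML. Its death rows for the two myeloma cohorts differ: 3, 3, 4, 6, 7 (naive) and 3, 3, 4 (refractory), against 2, 2, 2, 3, 3 and 2, 2, 2 in the Protocol. The SAP's version history says it is based on Protocol version 5.0; the current Protocol is version 8.0.

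**The concern.** The sentence describes the level for stopping a cohort on a safety concern. A cohort can be stopped by either row, so the quantity described is the chance that at least one row is crossed when toxicity is acceptable. If each row was given 5%, the cohort-level chance is not held at 5% by construction.

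The practical stake is how a crossing is read. The naive RRMM table matters most: it runs to n = 50, which equals the 10-subject lead-in plus the 40 GEN3014 subjects planned for Part B, and Protocol 9.6 confines the tables to GEN3014-treated subjects. A committee told that the cohort level is 5% would understate how often a stop signal appears in that cohort at acceptable toxicity. Any error runs toward stopping too readily, so it does not expose subjects to added risk.

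**Working it through.** **Inputs.** Looks and boundaries come from Protocol Tables 9-2 to 9-5 and SAP Tables 5-10 and 5-11. Acceptable rates are 10% for AE, and 1% (MM, DLBCL) or 5% (AML) for death. Neither document gives the spending formula or the association between the two counts, so both are assumptions here.

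**Step 1: how the rows were built.** I used the usual Pocock-type spending function, cumulative spend = α·ln(1 + (e − 1)t) with t = n/n_max. At each look the boundary is the smallest count that keeps the exact cumulative crossing probability within the spend.

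Example, naive AE row at n = 5: t = 0.1, so the spend is 0.05 × ln(1.1718) = 0.79%. At a 10% rate, P(X ≥ 3) = 0.86%, which is too large, and P(X ≥ 4) = 0.05%. The boundary is therefore 4, as printed.

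| Row | Printed in Protocol | Derived, 5% per row | Derived, 2.5% per row |
|---|---|---|---|
| Naive AE | 4,4,6,8,10 | 4,4,6,8,10 | 4,5,6,9,11 |
| Naive death | 2,2,2,3,3 | 2,2,2,3,3 | 2,2,3,3,3 |
| Refractory AE | 3,4,6 | 3,4,6 | 3,5,6 |
| Refractory death | 2,2,2 | 2,2,2 | 2,2,2 |
| DLBCL AE | 3,4,6,9 | 3,4,6,9 | 4,5,6,9 |
| DLBCL death | 2,2,2,3 | 2,2,2,3 | 2,2,3,3 |
| AML AE | 3,4,6 | 3,4,6 | 3,5,6 |
| AML death | 2,3,4 | 3,3,4 | 3,3,4 |

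A separate 5% per row reproduces seven of eight rows; an even split reproduces one. The exception is the AML death row. At n = 5 and a 5% rate, P(X ≥ 2) = 2.26% against a spend of 1.79%, so the printed 2 exceeds what the function allows at that look.

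**Step 2: the level of each row, and of either row.** I followed the two counts jointly from look to look, removing paths that had already crossed. In the nested case every treatment-related death also counts as a Grade ≥4 event. Independent and disjoint counts show the range.

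| Cohort (Protocol rows) | AE row alone | Death row alone | Either, nested | Either, independent | Either, disjoint |
|---|---|---|---|---|---|
| Naive RRMM | 4.46% | 2.55% | 6.55% | 6.90% | 6.93% |
| DLBCL | 3.45% | 2.05% | 5.17% | 5.42% | 5.44% |
| AML | 2.44% | 3.73% | 5.09% | 6.09% | 6.13% |
| Refractory RRMM | 2.44% | 1.69% | 3.91% | 4.09% | 4.10% |

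**Step 3: dependence on the AML n = 5 boundary.** With the derived row 3,3,4 in place of 2,3,4, the AML figure is 3.8% nested and 4.6% independent, both below 5%. This is a sensitivity check, not a proposal.

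**Step 4: the SAP rows.** With the SAP's myeloma death rows at the stated 1% rate, the death row contributes about 0.01%. The either-row figure is then 4.5% in naive RRMM and about 2.4% in refractory RRMM. DLBCL and AML are unchanged at 5.2% and 5.1%. Running the Step 1 derivation at a 5% death rate returns exactly 3,3,4,6,7 and 3,3,4. The SAP rows therefore correspond to a 5% death rate, although SAP 5.7.3 states 1% for myeloma.

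**The case against.** In group-sequential usage an overall level normally means accumulated over looks for one criterion. Read that way the sentence is true: every row is at or below 4.5%. The committee also sees which row was crossed, and that row's own level is below 5%. The tables are guidance, and for deaths the text says only that stopping will be considered. The figures place both true rates exactly at their limits; halving the death rate alone gives 4.9% (naive), 3.9% (DLBCL) and 2.9% (AML). All of this stands, and it makes the point one of wording. It does not remove the point, because the sentence speaks of the cohort and of a safety stop, and neither document says per criterion.

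Three stronger readings are tempting and are not supported.

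- **That each row spends a full 5%.** That would give 1 − 0.95² = 9.75% in every cohort. Each row was allotted 5%, but none attains it.
- **That the literal grade 4 wording in 9.6 raises the acceptable rate of counted events.** Adding deaths on top would make it 11% (MM, DLBCL) or 15% (AML), with combined levels of 9.0% in naive RRMM and 11.7% in AML. But the Protocol synopsis ties the guidance to Grade ≥4 events, every table row says Grade ≥4, and the AE rows reproduce at 10%. The wording is loose shorthand.
- **That three of four cohorts materially exceed 5%, in both documents.** DLBCL and AML exceed it by 0.2 and 0.1 points on the nested count, the AML excess rests on one boundary, and under the SAP rows naive RRMM does not exceed it.

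**Conclusion.** The point holds as a minor misstatement. The per-cohort 5% in Protocol 9.6 is not a property of the printed tables, because each criterion has its own 5% budget. The one clear excess is naive RRMM, at 6.6% (up to 6.9% across the association assumptions), about 1.3 times the stated level. DLBCL is marginally above 5%. AML is marginally above it on the nested count, and only with the printed n = 5 death boundary. Refractory RRMM is below 5% throughout.

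These figures assume both true rates at the acceptable limits, looks at the planned sample sizes, and 10% as the rate of Grade ≥4 events including deaths. The reconstruction in Step 1 also assumes the standard Pocock-type function, which the seven exact matches support.

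The recomputation also exposes two discrepancies that bear on any restated figure: the Protocol and SAP disagree on the myeloma death rows while stating the same 1% rate, and the AML death row departs at n = 5 from the method that reproduces the others. The documents do not settle which values were intended.

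**What to change.** Reconcile first: the Protocol and SAP myeloma death rows, the stated 1% death rate, and the AML death boundary at n = 5. Which values should stand is for the sponsor and its committees to decide.

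Then, in Protocol 9.6 and SAP 5.7.3:

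- state the level as 5% for each of the two criteria within a cohort;
- add the combined either-criterion figure for each cohort, computed from the reconciled rows, with the assumption about how the two counts overlap;
- write Grade ≥4 in the sentence giving the 10% acceptable rate, so that it names the event the tables count.

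The rewording is about two sentences per document, plus the reconciliation. The downside is that the stated level becomes slightly less favourable.

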**Table 9-2 Stopping Guidance for RRMM anti-CD38 mAb-naïve**

	n=5	n=10	n=20	n=35	n=50
Grade $\geq 4$ Treatment-Related AE (stop if $\geq$ )	4	4	6	8	10
Treatment-Related Death (stop if $\geq$ )	2	2	2	3	3

AE=adverse event; CD=cluster of differentiation; mAb=monoclonal antibody; RRMM=relapsed or refractory multiple myeloma.

**Table 9-3 Stopping Guidance for RRMM anti-CD38 mAb-refractory**

	n=5	n=10	n=20
Grade $\geq 4$ Treatment-Related AE (stop if $\geq$ )	3	4	6
Treatment-Related Death (stop if $\geq$ )	2	2	2

AE=adverse event; CD=cluster of differentiation; mAb=monoclonal antibody; RRMM=relapsed or refractory multiple myeloma.

**Table 9-4 Stopping Guidance for R/R DLBCL**

	n=5	n=10	n=20	n=40
Grade $\geq 4$ Treatment-Related AE (stop if $\geq$ )	3	4	6	9
Treatment-Related Death (stop if $\geq$ )	2	2	2	3

AE=adverse event; R/R DLBCL=relapsed or refractory diffuse large B-cell lymphoma.

**Table 9-5 Stopping Guidance for R/R AML**

	n=5	n=10	n=20
Grade $\geq 4$ Treatment-Related AE (stop if $\geq$ )	3	4	6
Treatment-Related Death (stop if $\geq$ )	2	3	4

AE=adverse event; R/R AML=relapsed or refractory acute myeloid leukemia.

## **10 SUPPORTING DOCUMENTATION AND OPERATIONAL CONSIDERATIONS**

### **10.1 Appendix 1: Regulatory, Ethical, and Trial Oversight Considerations**

The principles of the Declaration of Helsinki, the consolidated ICH-GCP, and applicable regulations and national law(s) (eg, 21 CFR and European regulation 536/2014 for clinical trials) in the country(ies) where the trial takes place shall constitute the main reference guidelines for ethical and regulatory conduct.

ICH GCP E6(R2) is an international ethical and scientific quality standard for designing, conducting, recording, and reporting trials that involve the participation of human subjects. Compliance with this standard provides public assurance that the rights, safety, and well-being of trial subjects are protected, consistent with the principles that originated in the Declaration of Helsinki, and that the trial data are credible.

The protocol, protocol amendments, ICF, IB, and other relevant documents (eg, advertisements) must be submitted to an IRB/IEC by the investigator and reviewed and approved by the IRB/IEC before the trial is initiated.

Any amendments to the protocol will require IRB/IEC approval before implementation of changes made to the trial design, except for changes necessary to eliminate an immediate hazard to trial subjects.

#### **10.1.1 Investigator Responsibilities**

The investigator is responsible for ensuring that the trial is performed in accordance with the protocol, ICH GCP E6(R2), and applicable regulatory and country-specific requirements. This includes supervision of the trial and staff. Delegation of responsibilities should be to only qualified staff and should be documented. In case the investigator is unavailable (eg, on vacation), the investigator should assure that a qualified, trained deputy physician is available for medical care of the subjects. Handover of information must be ensured and documented. The investigator shall notify the sponsor of any serious breach of ICH GCP E6(R2), the protocol or any regulation where required immediately.

#### **10.1.2 Independent Ethics Committee or Institutional Review Board**

This trial will be undertaken only after the IEC/IRB has given written approval of the final protocol, amendments to the protocol (if applicable), the ICF, applicable recruiting materials, and subject compensation programs, and the sponsor has received a copy of this written approval. This approval letter must be dated and must clearly identify the IEC/IRB and the documents being approved.

For all protocol amendments (excluding the ones that are purely administrative, with no consequences for subjects, data or trial conduct), the amendment and applicable ICF revisions must be submitted promptly to the IEC/IRB for review and written approval before implementation of the change(s).

The IB and updates to the IB, unexpected SAEs where a causal relationship cannot be ruled out, serious breaches, serious non-compliance, annual written summaries of the trial status, deviations to the protocol implemented to eliminate immediate hazards to the subjects must be submitted to the IEC/IRB.

Interim reports on the trial and/or review(s) of trial progress will be submitted by the investigator, where applicable, to the IEC/IRB at intervals stipulated in its guidelines.

At the end of the trial, the investigator (or sponsor where required) will notify the IEC/IRB about the trial completion, within the required timelines.

### **10.1.3 Financial Disclosure**

Investigators and sub-investigators will provide the sponsor with sufficient, accurate financial information as requested to allow the sponsor to submit complete and accurate financial certification or disclosure statements to the appropriate regulatory authorities. Investigators are responsible for providing information on financial interests during the course of the trial and for 1 year after completion of the trial.

### **10.1.4 Administrative Procedures**

#### **Protocol Amendments**

Neither the investigator nor the sponsor will modify this protocol without a formal amendment by the sponsor. Approval must be obtained from the IRB/EC and regulatory authorities (as locally required) before implementation of any changes, except for changes necessary to eliminate an immediate hazard to patients or changes that involve logistical or administrative aspects only (eg, change in the sponsor's Medical Monitor or contact information). Documentation of amendment approval by the investigator and IEC/IRB must be provided to the sponsor. When the change(s) involves only logistic or administrative aspects of the trial, the IRB (and IEC where required) only needs to be notified.

During the course of the trial, in situations where a deviation from the protocol is unavoidable, the investigator or other physician in attendance will contact the sponsor (see the separate Sponsor Contact Information page). Except in emergency situations, this contact should be made before implementing any deviations from the protocol. In all cases, contact with the sponsor must be made as soon as possible to discuss the situation and agree on an appropriate course of action. The data documented in the eCRF and source documents will reflect any deviation from the protocol, and the source documents will describe this departure and the circumstances requiring it.

#### **Regulatory Documentation**

This protocol and any amendments must be submitted to the appropriate regulatory authorities in each respective country, in accordance with local regulations. A trial may not be initiated until all local regulatory requirements are met.

#### **Subject Identification, Enrollment, and Screening Logs**

The investigator agrees to complete a subject identification log to permit easy identification of each subject during and after the trial. This document will be reviewed by the sponsor trial-site contact for completeness.

The subject identification log will be treated as confidential and will be filed by the investigator in the Investigator Site file and will never be transferred to the sponsor or any third parties. To ensure subject confidentiality, no copy will be made. All reports and communications relating to the trial will identify subjects by their subject number (or Screening number if not enrolled).

The investigator must also complete a subject screening log, which reports on all subjects who were seen to determine eligibility for inclusion in the trial.

### **10.1.5 Informed Consent Process**

The ICF(s) that is/are used must be approved by the sponsor and by the reviewing IEC/IRB and be in a language that the subject can read and understand. The ICF should be in accordance with principles that originated in the Declaration of Helsinki, ICH GCP E6(R2), applicable regulatory requirements, and sponsor policy.

It is the personal responsibility of the investigator or an authorized member of the trial-site personnel to explain to potential subjects (or his/her legally acceptable representatives) the aims, methods, reasonably anticipated benefits, and potential hazards of the trial, and any discomfort participation in the trial may entail.

Subjects will be informed that their participation is voluntary and that they may withdraw consent to participate at any time without justifying the reason. They will be informed that choosing not to participate will not affect the care the subject will receive for the treatment of their disease. Subjects will be told that alternative treatments are available if they refuse to take part and that such refusal will not prejudice future treatment. Finally, they will be told that the investigator will maintain a subject identification register for the purposes of long-term follow up if needed and that their records may be accessed by health authorities and authorized sponsor personnel without violating the confidentiality of the subject, to the extent permitted by the applicable law(s) or regulations.

By signing the ICF the subject (or legally authorized representative) is authorizing such access, including permission to obtain information about survival status, and agrees to allow their trial physician to re-contact the subject for the purpose of obtaining consent for additional safety evaluations, if needed, [and subsequent disease-related treatments, or to obtain information about survival status].

The subject (or his/her legally acceptable representatives) will be given sufficient time to read the ICF and the opportunity to enquire about details of the trial prior to deciding whether to participate in the trial. After this explanation and before any trial-specific procedure is performed, consent should be appropriately documented by means of the subject's personally dated signature.

Subjects (or his/her legally authorized representative) will be required to sign a statement of informed consent that meets the requirements of 21 CFR 50, local regulations, ICH guidelines, Health Insurance Portability and Accountability Act (HIPAA) and EU General Data Protection Regulation (GDPR) requirements, where applicable, and the IRB/IEC or trial center. The investigator or authorized person obtaining the informed consent must also sign and date the ICF. After having obtained the consent, a copy of the ICF must be given to the subject.

If the subject is unable to read or write, an impartial witness should be present for the entire informed consent process (which includes reading and explaining all written information) and should personally date and sign the ICF after the oral consent of the subject is obtained.

Subjects must be re-consented to the most current version of the ICF(s) during their participation in the trial.

Subjects who are rescreened are required to sign a new ICF if updates have been made since signing the most recent ICF.

A separate ICF will be used for the required DNA/RNA research component of the trial if required by local regulations.

